14.9. Medical Monitor

The Sponsor will utilize an independent Medical Monitor to provide individual serious adverse event adjudication for the trial. It is anticipated that the Medical Monitor will meet with the Sponsor on a periodic basis, or as needed, depending on the rate of patient accrual. The primary responsibilities of the Medical Monitor are to:

- Review serious adverse events that occur over the course of the trial and the subsequent classification of these adverse events as related to the device
- Review donor and recipient treatment group eligibility issues.
- Evaluate possible protocol deviations.
- Provide oversight for issues affecting general patient welfare.
- Provide recommendations to extend the length of follow-up past 30 days post-transplant for a subject experiencing a serious adverse event.
- Review all site reported EAD diagnosis based on the pre-specified protocol criteria and actual clinical case of the trial patient.

14.10. Stopping Rule

The stopping rule will be confirmed every time a trigger event occurs (i.e., each time a subject in either arms has experienced an early liver dysfunction or death). In addition, Stopping rule analyses will be conducted twice, once after the first 10 transplanted liver recipients in Part A of the study have completed 30 days post-transplantation and a second time after the 20 transplanted liver recipients in Part A of the study have completed 30 days post-transplantation. The stopping rule will be based on the occurrence of either early liver graft dysfunction within 7 days or death within 30 days post-transplantation. The null and alternative hypotheses to be tested are as follows:

$$H_{40}: \pi_{3, \text{OCS}} \leq \pi_{3, \text{CONTROL}} \text{ and}$$

$$H_{41}: \pi_{3,OCS} > \pi_{3,CONTROL},$$

where $\pi_{3,OCS}$ and $\pi_{3,CONTROL}$ are the true proportions of subjects with either early liver graft dysfunction within 7 days or death within 30 days post-transplantation for the OCS and Control treatments, respectively. A one-sided Fisher's Exact Test will be conducted to test the null hypothesis H_{40} , and the study will be stopped if the p-value is less than 0.15.

The table below provides an example indicating the circumstances under which we would stop the study and those under which we would continue the study for the analysis to be performed after the 20 transplanted liver recipients in Part A of the study have completed 30 days post-transplantation, assuming 10 recipients in each treatment group.

Conditions Under which the Study Would be Stopped									
Number of CONTROL Patients Experiencing an Event	Number of OCS Patients Experiencing an Event								
	0	1	2	3	4	5	6	7	8
0	Cont.	Cont.	Cont.	Stop	Stop	Stop	Stop	Stop	Stop
1	Cont.	Cont.	Cont.	Cont.	Stop	Stop	Stop	Stop	Stop
2	Cont.	Cont.	Cont.	Cont.	Cont.	Stop	Stop	Stop	Stop
3	Cont.	Cont.	Cont.	Cont.	Cont.	Cont.	Stop	Stop	Stop
4	Cont.	Cont.	Cont.	Cont.	Cont.	Cont.	Cont.	Stop	Stop
5	Cont.	Cont.	Cont.	Cont.	Cont.	Cont.	Cont.	Cont.	Stop
6	Cont.	Cont.	Cont.	Cont.	Cont.	Cont.	Cont.	Cont.	Cont.
7	Cont.	Cont.	Cont.	Cont.	Cont.	Cont.	Cont.	Cont.	Cont.
8	Cont.	Cont.	Cont.	Cont.	Cont.	Cont.	Cont.	Cont.	Cont.

Key: Note: Cont. = Continue

TransMedics will be responsible for implementing the stopping rule and will stop the trial if a stopping rule was triggered until the data is reviewed by the DMB.

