3.1. Type of the Trial

A prospective, multi-center, randomized, controlled Phased Pivotal trial with transplanted recipients assigned to either the OCS Liver arm (OCS - treatment) or standard of care cold storage arm (SOC - control). The trial will have two parts. (Part A rolling into large Part B, assuming stopping rule is not triggered):

- Part A: Include the first 20 randomized transplanted liver recipients with pre-specified stopping rule to ensure safety;
- Part B: assuming no stopping rule was triggered, the trial enrollment will continue beyond the initial 20 transplanted recipients in Part A into Part B, while the data from the first 20 subjects is being reviewed. All of the final analyses of the study will be based on the pooled data from Parts A and B.

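### Section 14.10 sets no end to the event-triggered stopping check at p<0.15: the chance of a false trigger is about 7-12% if it ends with Part A and about 37-42% if followed literally to 300 subjects.

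*Protocol*

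**What the plan says.** Protocol 14.10 sets two kinds of check.

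- **Event-triggered.** "The stopping rule will be confirmed every time a trigger event occurs (i.e., each time a subject in either arms has experienced an early liver"; the words cut off name graft dysfunction and death. No last subject, part or date is given.
- **Scheduled.** "In addition, Stopping rule analyses will be conducted twice, once after the first 10 transplanted liver recipients in Part A" have completed 30 days, and again after 20. Only these two analyses are limited to Part A.

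The event is the same for both: "The stopping rule will be based on the occurrence of either early liver graft dysfunction within 7 days or death within 30 days post-transplantation". So are the test ("A one-sided Fisher's Exact Test will be conducted to test the null hypothesis" that OCS is no worse than Control) and the threshold: "the study will be stopped if the p-value is less than 0.15". Nothing adjusts for repeated testing. The sponsor implements the rule, and a trigger stops the trial until the DMB has reviewed the data.

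Protocol 3.1 describes the rule as belonging to the first phase: "Part A: Include the first 20 randomized transplanted liver recipients with pre-specified stopping rule to ensure safety". Part B follows provided that the rule has not fired. The synopsis and SAP 3.1 say the same. SAP 5.6 lists only descriptive Part A summaries for the FDA and does not mention the event-triggered check.

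**The concern.** A loose threshold of 0.15 can be reasonable for an early safety gate on 20 recipients. It behaves very differently when the same test is repeated, unadjusted, at every event over 300. The sponsor's staff working from 14.10 alone would find no instruction to stop testing after recipient 20. Enrollment also runs on into Part B while the Part A data are under review, so nothing in the conduct of the trial marks the boundary for them.

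At stake are avoidable stops of a trial whose arms do not differ. The sponsor would also hold a running comparison by arm, to the end of an unblinded trial, on an event that largely overlaps the primary endpoint. The protocol gives no operating characteristics for the rule under either reading.

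**Working it through.** **Inputs.** One-sided Fisher's exact test, halt if p<0.15 (14.10). Checks at every event in either arm and at recipients 10 and 20 (14.10). Allocation 1:1 (9.5). Total 300 transplanted (9.6). The documents give no event rate for EAD or 30-day death, so equal rates of 0.15 to 0.30 are an assumption, set around the EAD design rates of 0.20 (OCS) and 0.25 (Control) in 9.6.

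**Step 1: the plan's own table (10 per arm).** With *o* OCS events and *c* Control events, and m = o + c, the one-sided p is the sum over x ≥ o of C(10,x)·C(10,m−x)/C(20,m).

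- c=0, o=2: C(10,2)/C(20,2) = 45/190 = 0.237. Printed Continue; agrees.
- c=0, o=3: C(10,3)/C(20,3) = 120/1140 = 0.105. Printed Stop; agrees.
- c=1, o=4: (210×10 + 252)/15504 = 2352/15504 = 0.152. Printed Stop, but p is not below 0.15.

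Over all 81 cells, 76 agree with p<0.15. The five that do not (Control/OCS events) are 1/4 (p=0.152), 2/5 (0.175), 3/6 (0.185), 4/7 (0.185) and 5/8 (0.175), all printed Stop. A cut-off of 0.20 reproduces every cell. The table therefore does not follow the stated threshold, and this affects which probability can be quoted for the rule.

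**Step 2: number of checks.** If EAD alone occurs in 20-25% of subjects, 300×0.20 = 60 and 300×0.25 = 75 event-triggered checks would be made by the end of enrollment.

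**Step 3: probability of at least one trigger at p<0.15 when the arms do not differ.** Monte Carlo, outcomes treated as known in order of transplant, 4,000 to 15,000 runs per setting (simulation standard error 0.4 to 0.8 points). Block size is not given; for the 300-subject runs, blocks of four and simple randomization gave much the same result.

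| Equal event rate | Two scheduled looks only | Every event, ending at 20 | Every event, to 300 |
|---|---|---|---|
| 0.15 | 5% | 7% | 37% |
| 0.20 | 6% | 9% | 38-40% |
| 0.225 | 6.5% | 10% | 40% |
| 0.25 | 7% | 11% | 40-42% |
| 0.30 | 7% | 12% | 42% |

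**Step 4: design rates (0.20 OCS, 0.25 Control).** About 6-7% if the checks end at 20, and about 19% if they run to 300.

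**Step 5: sensitivity to the table.** With the 0.20 cut-off that reproduces the table, and a rate of 0.25 in both arms, the figures rise to about 15% by recipient 20 and about 50% by 300. At the single 10 v 10 look alone, the exact stopping probability is 4.8% under p<0.15 and 9.6% under the 0.20 cut-off.

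**The case against.** The strongest objection is that the documents point to a rule for Part A only. Three sections attach it to the first 20 recipients and make it the gate into Part B. Both scheduled analyses and the worked table concern Part A, and the SAP plans no stopping-rule test in Part B. On that reading the false-trigger figure is 7-12%, and only an end-point clause is missing. This stands: Part A only is the better-supported reading, and the 37-42% is conditional on taking 14.10 literally.

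Second, a trigger is a pause. The DMB reviews the data and recommends continuation, modification or termination (14.11), and a false trigger gives OCS no extra chance of being declared non-inferior. That also stands. How sensitive a safety pause should be is partly a matter of preference.

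Neither objection removes the gap. Section 14.10 is the operative text, it makes the event-triggered check recur without limit, and it confines only the additional analyses to Part A.

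A reader might infer that 3.1 and 14.10 prescribe different rules for Part B. They do not: 3.1 sets no Part B rule and 14.10 never mentions Part B. A reader might also take the checks for repeated tests of the primary endpoint. The tested event is EAD within 7 days or death within 30 days, whereas the primary endpoint is EAD or primary non-function in the first 7 days.

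**Conclusion.** The point holds as an unstated end to a decision rule whose behavior depends heavily on where it ends. With equal event rates of 0.15-0.30, the probability of at least one false trigger is about 7-12% if the checks stop with Part A and about 37-42% if they continue through 300 subjects. Under the design rates it is about 6-7% and 19%.

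These figures assume p<0.15 as written, 1:1 allocation, outcomes known in order of transplant, and event rates borrowed from the EAD design assumptions. The result changes little over the range of rates tried.

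It would be tempting to conclude that the plan terminates two in five trials of an equivalent device. The documents do not support that: the literal Part B reading is the less likely intention, and a trigger leads to DMB review and not to automatic termination.

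**What to change.** State in 14.10 that the event-triggered check and its p<0.15 threshold apply to the first 20 transplanted recipients and end with the second Part A analysis, consistent with 3.1. State also that Part B is monitored by the DMB under 14.11.

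Separately, reconcile the stopping table with the p<0.15 threshold. Print no false-trigger probability before that is done; then report the figure for the boundary that is kept.

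The cost is two sentences in 14.10 and a correction to either the table or the threshold. The downside is that Part B has no automatic sponsor-run trigger. The DMB's remit there already covers the safety data and the primary effectiveness and safety endpoints.

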9.6. Sample Size Determination

The sample size for this trial was determined based on the primary effectiveness endpoint, Early Liver Allograft dysfunction (EAD) in the first 7 days post-transplantation. The sample size calculation assumed a one-sided, normal approximation test for non-inferiority, an alpha level of 0.05, a non-inferiority margin of 0.075, a 1:1 allocation, true proportions for the primary effectiveness endpoint of 0.2 for the OCS treatment and 0.25 for the Control treatment, and power of 80%. Based on these specifications, the required sample size was determined to be 144 transplanted recipients per treatment group, or 288 total transplanted subjects. To ensure an adequate number of subjects in the Per Protocol Population, the sample size was increased to a total of 300 transplanted subjects. Subjects will be enrolled until there are either 290 subjects in the Per Protocol Population or a total of 300 transplanted subjects, whichever comes first.

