3.5. Changes to the Protocol-Specified Analyses

The sample size re-estimation proposed in the protocol will not be performed per FDA recommendation. Enrollment will be concluded at the original planned sample size of 300 patients as FDA has recommended ([REDACTED]).

As recommended by FDA, additional post-hoc exploratory analyses for the primary endpoint have been added to test for site poolability, with small sites pooled by US geographic region. ([REDACTED]).

Post-hoc tipping point sensitivity analyses have been added based on FDA's recommendation for the primary efficacy endpoint and the two secondary efficacy endpoints ([REDACTED]).

Two exploratory study populations have been added to the analyses. The exploratory mITT2 population will include an additional 43 subjects who have been transplanted off-study with a randomized organ, and the exploratory ITT population will include all subjects who have signed informed consent, been enrolled in the study, randomized, and the assigned liver preservation method has been initiated. An Exploratory analysis will be included for the mITT2 and ITT populations of patient and graft survival at 30 days post-transplant. ([REDACTED]).

Analyses of the primary effectiveness endpoints and secondary effectiveness endpoints by donor inclusion criteria will be performed.

The incidence of non-ischemic biliary complications in 30 days and in 6 months, defined using MedDRA terminology, will be reported ([REDACTED]).

Subgroup reporting has been added for Donor after Brain Death (DBD) transplants. The two subgroups used in recipient reporting are DBD transplants with total cross clamp time \geq 6 hours and DBD transplants with total cross clamp time $<$ 6 hours ([REDACTED]).

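### The Part A stopping rule (one-sided Fisher p < 0.15) and its own example table disagree in five of 81 cells; in all five the table stops and the text continues

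*Protocol*

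**What the plan says.** Protocol section 14.10 defines the event as early graft dysfunction within 7 days or death within 30 days. The null hypothesis is that the OCS rate is no higher than the Control rate. It is tested with a one-sided Fisher's exact test, and "the study will be stopped if the p-value is less than 0.15".

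A table follows: "The table below provides an example indicating the circumstances under which we would stop the study". It applies to the analysis after all 20 Part A recipients have reached day 30, "assuming 10 recipients in each treatment group". Rows are Control events 0 to 8 and columns are OCS events 0 to 8. The first stop appears at 3, 4, 5, 6, 7 and 8 OCS events for 0, 1, 2, 3, 4 and 5 Control events. Rows 6 to 8 contain no stop. That makes 21 stop cells.

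The rule is also applied after the first 10 recipients and at each event: "The stopping rule will be confirmed every time a trigger event occurs". The sponsor implements it and "will stop the trial if a stopping rule was triggered until the data is reviewed by the DMB". Under Protocol section 3.1, enrolment otherwise runs on into Part B "while the data from the first 20 subjects is being reviewed". SAP section 3.1 mentions the stopping rule but gives neither a threshold nor a table.

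**The concern.** The test, its direction, the arm sizes and the threshold are all stated, so each cell has exactly one correct entry. The printed stops start wherever OCS has three more events than Control. One-sided Fisher p-values are not constant along that diagonal, so the pattern was worth checking against 0.15.

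If the two disagree, some Part A results call for a safety pause under one reading and for continued enrolment under the other. The sponsor has to act on one of them, and the protocol does not say which governs.

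**Working it through.** **Inputs.** Test, direction, threshold, arm sizes (10 and 10) and table entries come from Protocol section 14.10. Design event rates come from Protocol section 9.6: "true proportions for the primary effectiveness endpoint of 0.2 for the OCS treatment and 0.25 for the Control treatment". These are EAD rates, used here as a stand-in for EAD or death. Other OCS rates below are assumptions.

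**Formula.** With *o* OCS events, *c* Control events and *k* = *o* + *c*,

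p = Σ C(10, x) · C(10, k − x) / C(20, k), summed over x from *o* to min(10, k).

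**Step 1: cells that agree.**
- 0 Control v 3 OCS: 120/1140 = 0.1053, below 0.15; the table says stop.
- 0 v 2: 45/190 = 0.2368, above 0.15; the table says continue.

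**Step 2: cells that disagree.**

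| Control v OCS events | Calculation | p | Text | Table |
|---|---|---|---|---|
| 1 v 4 | (210·10 + 252)/15504 | 0.1517 | continue | stop |
| 2 v 5 | (252·45 + 210·10 + 120)/77520 | 0.1749 | continue | stop |
| 3 v 6 | (210·120 + 120·45 + 45·10 + 10)/167960 | 0.1849 | continue | stop |
| 4 v 7 | (120·210 + 45·120 + 10·45 + 10)/167960 | 0.1849 | continue | stop |
| 5 v 8 | (45·252 + 10·210 + 120)/77520 | 0.1749 | continue | stop |

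The remaining 76 cells agree, and no cell differs in the other direction. The text gives 16 stop cells and the table 21.

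**Step 3: what cut-off the table does fit.** The largest p in a stop cell is 0.1849 and the smallest in a continue cell is 0.2368. Any rule of p below a cut-off greater than 0.1849 and no greater than 0.2368, for example 0.20, reproduces all 81 cells.

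**Step 4: could a different test at 0.15 explain it?** No. The number of cells that differ from the table is:
- two-sided Fisher: 9
- mid-p: 1
- pooled z: 2
- continuity-corrected z: the same 5

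**Step 5: chance of a halt at the 20-recipient look.** Sum the product of two binomial(10) probabilities over the stop cells, extending the table to 9 and 10 OCS events. The Control rate is 0.25 throughout.

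| OCS rate | Text | Table | Sum of the five cells |
|---|---|---|---|
| 0.20 (design) | 0.0263 | 0.0518 | 0.0255 |
| 0.25 (assumed) | 0.0479 | 0.0963 | 0.0484 |
| 0.35 (assumed) | 0.1222 | 0.2307 | 0.1084 |
| 0.40 (assumed) | 0.1782 | 0.3165 | 0.1383 |
| 0.50 (assumed) | 0.3280 | 0.5068 | 0.1788 |

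**Step 6: checks that have no table.**
- 10-recipient look, assuming 5 v 5: cut-offs of 0.15 and 0.20 give the same decision in all 36 cells. But 0 v 2 has p = 10/45 = 0.2222, which is inside the range the table leaves open.
- 9 OCS and 11 Control recipients: 0 Control v 2 OCS events gives p = 36/190 = 0.1895, which continues at 0.15 and stops at 0.20.

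**The case against.** The best counter-argument accepts the arithmetic and disputes its weight.

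- **The table is only an example; the words carry the rule.** The threshold is stated once, clearly, and can be applied at any check and any split. That is a reasonable reading, but the protocol does not say it. The example is for a planned look with the stated arm sizes, so it should obey the rule.
- **Rounding.** Only 1 v 4 is close, and even 0.15 is not less than 0.15. The other four are 0.175 to 0.185.
- **Repeated checks shrink the gap.** This stands. Suppose a 10/10 split, events known at once in transplant order, and a check at each event and at 10 recipients. In simulation, about half of the paths that end in a disputed cell would then already have triggered the text rule. On those assumptions the gap in ever having triggered falls to roughly half: about 1.3 points rather than 2.6 at the design rates, and about 9 rather than 17.9 at an OCS rate of 0.50. A reporting lag would change this. A trigger only pauses the trial until board review, so the 20-recipient look can still yield opposite decisions.
- **The larger figures use assumed rates.** True: OCS rates of 0.25 to 0.50 are not in the documents. They show how the rule behaves when a safety rule is most needed.
- **Limited consequence.** Also true. Following the table cannot miss a stop that the text requires, a pause does not end the trial, the board reviews safety periodically in any case, and Part A is probably over.

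**Conclusion.** The contradiction is real and exact. Section 14.10 gives two decision rules that differ in five of 81 cells, always with the table stopping and the text continuing, and neither document says which prevails. The cell count and the p-values need no assumption beyond the stated 10 per arm.

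At the single 20-recipient look the table roughly doubles the chance of a halt at the design rates (2.6% to 5.2%). At an assumed OCS rate of 0.50 it adds 17.9 percentage points. These figures use EAD as a proxy for the composite event, require an even split, and leave out the earlier event-driven checks, which would reduce the gap.

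The point should be fixed because it concerns the trigger of a pre-specified safety rule. It does not touch any final analysis. The documents do not show which version was intended, and this review does not choose.

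**What to change.** Reconcile the threshold and the table in section 14.10 so that each reproduces the other. State which governs at every check, including the 10-recipient look, the event-driven checks and any uneven split, none of which the table covers.

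SAP section 3.5 says "Enrollment will be concluded at the original planned sample size of 300 patients", which suggests that Part A is already complete. If so, a note to file or a sentence in the clinical study report should record which version was applied and whether any observed result, at any check, fell where the two differ.

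The cost is a wording change or a short note; no data collection or analysis changes.

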14.11. Data Monitoring Board

An independent Data Safety Monitoring Board (DMB) will be established by the Sponsor to periodically assess the progress of the trial, the safety data and the primary effectiveness and safety endpoints. The DSMB will make recommendations to the Sponsor regarding continuation, modification or termination of the clinical trial. The DMB will review all data submitted to them by the Sponsor and may request additional information to assist in their decision process. They will attend scheduled meetings and issue written minutes of their meetings; furthermore, the appointed Chair will be responsible for issuing final written recommendations.

14.12. Investigator Training

Device, protocol and electronic database training will be provided to all the participant investigators and support staff prior to patient enrollment in the trial. Device training will be conducted at the TransMedics clinical training facility or equivalent training facility. Protocol training will include a thorough review of this protocol. Electronic database training will consist of an explanation of the structure of the database, the data elements to be collected, simulated use of the database, error handling, and instructions regarding the handling of queries.

16. AMENDMENT POLICY

The investigator will not make any changes to this protocol without prior written consent from the Sponsor and subsequent approval by the IRB or EC, except if the deviation from the protocol is necessary to protect the life and physical well-being of a subject in an emergency. Such protocol deviations will be reported to the Sponsor and the reviewing IRB or EC as soon as possible, but no later than 5 working days after the emergency occurred. Any permanent change to the protocol, whether it is an overall change or a change for specific trial center(s), will be handled as a protocol amendment. Any amendment to the protocol that appears indicated as the trial progresses will be fully discussed by the investigator(s) and the Sponsor. If agreement is reached regarding the need for an amendment, it will be written by the Sponsor. The written amendment will be submitted to the chairman of the IRB or EC responsible for reviewing amendments. Except for "administrative letters," investigators will await IRB or EC approval of protocol amendments before implementing the change(s). Administrative letters are defined to have no effect on the validity of the data or information resulting from the completion of the approved protocol, or the relationship of likely patient risk to benefit relied upon to approve the protocol; the scientific soundness of the investigational plan or protocol; and, the right, safety or welfare of the human subjects involved in the investigation. The Sponsor will notify the FDA of such changes in a 5-Day Notice. When, in the judgment of the IRB or EC, the investigators and/or the Sponsor, the amendment to the protocol substantially alters the trial design and/or increases the potential risk to the subject; such changes will be approved by the FDA and the IRB and EC.

